**SYSTEMATIC INVESTIGATION OF BLACKS WITH STROKE- GENOMICS
(SIBS-GENOMICS) STUDY**

SEPTEMBER 5TH, 2022

PILOT TRIAL

Specific Aim. To determine the effectiveness of the Afrocentric stroke riskometer mobile phone application combined with the motivation stroke educational video and educational modules for improvement of individual awareness and reduction of the total quantitative risk of stroke through a randomized controlled trial among stroke-free adults in Nigeria and Ghana.

Study design: A feasibility pilot study involving stroke-free adults with at least 2 vascular risk factors for stroke assigned to an educational intervention for 2 months comprising of a stroke video and riskometer App aimed at improving stroke risk factor awareness and health seeking behavioural modification to control vascular risk (n=50) compared with a control group (n=50) who are offered one time counselling.

Study Sites: 3 sites across Nigeria and Ghana

Study Participants: Study participants will be CONSECUTIVELY selected from the existing pool of stroke-free controls in SIREN and SIBS Genomics studies across the 3 study sites (60 from Ibadan, 20 from Kumasi and 20 from Zaria). The vascular risk factor profile of these control participants has already been assessed. Stroke free status at enrollment will be reconfirmed using the locally validated version of the QVSFS.

Eligibility criteria: **Inclusion criteria:** (i) male or female (sex is a biologic variable of interest), (ii) age \geq 18 years, (iii) with at least 2 stroke risk factors based on the list of 11 topmost modifiable risk factors identified in the SIREN study (including hypertension, diabetes mellitus, dyslipidemia, smoking, overweight, physical inactivity, or unbalanced/poor diet). (iv) ownership or access to smartphone in consenting stroke-free adults. **Exclusion criteria:** prior history of vascular disease (e.g., stroke, transient ischemic attack, angina, myocardial infarction, peripheral vascular disease, and atrial fibrillation), or cognitive impairment; not comfortable reading and writing, depression or other psychiatric disorders (through personal declaration) likely to affect the interventions; participation in another RCT; other conditions rendering the individual unsuitable to participate in this research as judged by treating physicians,

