Justification for Eligibility Criteria: Individuals with existing high modifiable risk are more likely to be motivated to engage in behavioral change activities more so than those without.

Recruitment: Research coordinators (RCs) will obtain informed consent, schedule baseline assessment & alert statistician of a new participant to be randomized via REDCap. Randomization will be performed within 24 hours & baseline assessments within one week at the respective SIREN facility/community. Baseline assessment will include screening of all participants for stroke risk factors by trained RCs. Risk factor screening will include measurement of blood pressure, blood glucose and lipid profile, psychosocial assessment for stress, dietary recall to assess salt intake and vegetable consumption, waist circumference and body mass index.

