Intervention: The app will not be installed on the smartphones during the pilot study to limit potential future exposure contamination. RCs will complete baseline screening assessment with participants and capture a screenshot of the individual's current global stroke risk score as a percentage, which will then be given to the participant via their smartphone (i.e., **screenshot of the score produced by the app**). Participants will be shown their risk scores and the specific risk factors identified through the screening. They will be asked to visit their doctors /primary care clinicians to facilitate management their risk factors through therapeutic lifestyle changes or pharmacotherapy, for example antihypertensives for hypertension, statins for dyslipidemia, or oral hypoglycemics for diabetes. This will be part of health seeking behaviour the app should promote, which will be assessed as part of process measure. Participants will receive monthly reminders on compliance/adherence to any clinician prescribed treatment or lifestyle modifications, as applicable, and to follow-up with primary provider if they haven't already and especially if their risks include hypertension, diabetes, or dyslipidemia. Participants will be asked to show their current global stroke risk to their clinician/doctor. As part of process measure, we will assess clinician acceptability and readiness to use the app to monitor their patients overall progress with total risk factor control. The records will be stored on our server, such that if they lose the score risk, the RC will be able to provide another copy (paper or digital) so their clinicians will still be able to access risk scores when shown by participants. In

addition, participants will be encouraged to watch the stroke video at least once monthly that will be shared via their smartphone, although they will be asked not to share it with others to minimize exposure beyond enrolled intervention participants.

Control group will be screened at baseline and be informed about their risk factors. They will be encouraged to seek medical therapy for a doctor after assessment of their baseline risk factors, should they have hypertension, diabetes, or dyslipidemia, but this advice will not be reinforced by either exposed to the app or the stroke video. They will complete a post-study questionnaire to assess any contamination with the intervention.

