Randomization: will be at individual level, per site as the app is meant to be developed at individual level eventually.

Concealment of allocation: Blinding of participants is not possible given the nature of the intervention. However, the adjudicator and the study statistician will not be aware of the allocation status of study participants during outcome data collection and analysis respectively. Outcome assessors will not be involved in delivering the intervention. To ensure blindness, trial participants will be told not to divulge details of their treatment to the assessors. The randomization scheme which will be used to allocate patients to groups will be developed & maintained by the lead study biostatistician. Randomization database will be independent & will not be accessible to outcome assessors or other personnel. Whereas the research coordinators (RCs) will be aware of the randomization assignment, they will not have any role in the delivery of the intervention or outcome adjudication.

Outcome measures:

1. **Feasibility measures:** Proportion approached, proportion refused, proportion ineligible (reasons for ineligibility), proportion enrolled, proportion completing follow-up, & proportion visiting their doctors will be compared between the two groups.
2. **Satisfaction and acceptability measures:** (i) autonomous self-regulation was assessed using the 15-item Treatment Self-regulation questionnaire,¹⁴ (ii) patient satisfaction using the telemedicine satisfaction and usefulness questionnaire, (iii) reported side effects of medications, (iv) hypertension and stroke knowledge using a 14 item questionnaire & (v) adherence measures to medications prescribed for primary prevention and lifestyle advice (physical activity, dietary patterns, alcohol and cigarette use); and participant preferences, insights, and challenges in using the app and efforts toward adopting behavioral change collected through and end of study key informant interview.
3. **Signal of Efficacy measures:** 1.) Change in total stroke risk score at month 2 calculated as difference between baseline score and month 2 score. 2) Change in stroke risk factor awareness score. 3) differences in number of encounters with healthcare provider during the period of the trial in those who have either hypertension, dyslipidemia or diabetes.

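### The total stroke risk score has no listed inputs; if self-reported items count, its unblinded month-2 comparison is open to differential reporting

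*Protocol*

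**What the plan says.** Under Outcome measures, item 3, the protocol gives three signals of efficacy. The only one that measures risk reduction is "Change in total stroke risk score at month 2 calculated as difference between baseline score and month 2 score". No list of inputs and no weights are given there or elsewhere.

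The score comes from the app at screening. Under Intervention: "RCs will complete baseline screening assessment with participants and capture a screenshot of the individual's current global stroke risk score as a percentage". What is screened is set out under Recruitment. Part is measured: "Risk factor screening will include measurement of blood pressure, blood glucose and lipid profile", together with waist circumference and body mass index. Part is the participant's own account: "psychosocial assessment for stress, dietary recall to assess salt intake and vegetable consumption". The risk factors named under Eligibility criteria also include "smoking, overweight, physical inactivity, or unbalanced/poor diet"; of these, smoking and physical activity are usually self-reported.

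On what participants know, Concealment of allocation states "Blinding of participants is not possible given the nature of the intervention". Under Intervention, "Participants will be shown their risk scores and the specific risk factors identified through the screening"; monthly reminders and a monthly prompt to watch the video follow. For the other arm, "Control group will be screened at baseline and be informed about their risk factors". Controls are also encouraged to seek care where they have hypertension, diabetes or dyslipidemia, but without the app or the video. The score and the reminders are not mentioned for them.

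**The concern.** A self-reported item can change because behaviour changed or because the answer changed. In an unblinded comparison the second possibility matters when the arms have been prompted differently. Here one arm has seen its score and been reminded each month, while the other has been told its risk factors once. If dietary recall or the stress assessment feeds the score, the difference in score change at month 2 cannot separate lower risk from different reporting.

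The safeguards under Concealment of allocation keep the adjudicator and statistician unaware of allocation, separate the assessors from delivery, and ask participants not to reveal their group. They protect the assessor's judgement. They do not protect an answer given by someone who knows their own allocation. The post-study questionnaire for controls looks for contamination, which is a different problem.

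The stake is what the pilot hands on. Statistical Analysis says the sample was chosen to give precise estimates for a later design. More participants narrow an interval but do not remove a bias, so a reporting effect would pass into the planning of the next trial as if it were risk reduction.

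**Working it through.** **Step 1. What is stated and what is inferred.**

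| Link in the argument | Status in the protocol |
|---|---|
| Efficacy measure 1 is one total score | Stated (Outcome measures, item 3) |
| The score is captured at the screening | Stated (Intervention) |
| The screening includes self-reported items | Stated (Recruitment) |
| Self-reported items enter the score | Inferred; inputs not listed |
| Weight of those items | Not given |
| Participants are unblinded | Stated (Concealment of allocation) |
| Only the intervention arm sees the score | Inferred from the arm descriptions |
| Controls learn their risk factors | Stated (Intervention) |

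The argument is therefore conditional: it holds if self-reported items carry weight. The items listed under Recruitment are blood pressure, glucose, lipids, waist and BMI (5 measured) and stress, salt and vegetables (3 self-reported). These are counts of items, not weights, and cannot be turned into a size of bias.

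**Step 2. No planned figure to reproduce.** The protocol gives 50 per arm but no SD, effect size, power or target width. No stated number is in dispute.

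**Step 3. Illustration of sensitivity (assumptions, not estimates).** Assume a normal approximation, two-sided alpha of 0.05 (the protocol does not state sidedness), 50 per arm and a true effect of zero. Let d be the shift in the intervention arm's mean change, in SD units of the change score, due to reporting alone.

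- Standard error of the difference: √(2/50) = 0.20 SD.
- 95% CI half-width: 1.96 × 0.20 = 0.39 SD.
- Chance of p < 0.05: Φ(d/0.20 − 1.96) + Φ(−d/0.20 − 1.96).

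| d (assumed) | Chance of p < 0.05 |
|---|---|
| 0 | 5.0% |
| 0.1 | 7.9% |
| 0.2 | 17.0% |
| 0.3 | 32.3% |
| 0.4 | 51.6% |
| 0.5 | 70.5% |

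For d = 0.2: Φ(1.00 − 1.96) + Φ(−1.00 − 1.96) = 0.1685 + 0.0015 = 0.170.

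**Step 4. Dependence on the unknown weight.** Suppose the self-reported part shifts by 0.5 SD and contributes to the total in proportion to a weight w, so that d = 0.5w.

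| w (assumed) | d | Chance of p < 0.05 |
|---|---|---|
| 0 | 0 | 5.0% |
| 0.10 | 0.05 | 5.7% |
| 0.25 | 0.125 | 9.6% |
| 0.50 | 0.25 | 24.0% |

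The consequence runs from nothing to substantial according to a weight the protocol does not give. The tables are symmetric in the sign of d and say nothing about direction.

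**The case against.** The strongest objection is that the premise is unproved. No section says that stress or diet enters the score, and not every screened item need do so. This stands, and the point is worded conditionally for that reason.

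Second, the arms are less different than they look. Controls are screened, told their risk factors and advised to seek care, so they too may answer differently later. Intervention participants receive a percentage and their identified factors, not the weights. The reminders also cover prescribed treatment and provider follow-up, not lifestyle alone. This stands too: the exposure is unequal, not present in one arm and absent in the other.

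Third, a reader might infer that an observed reduction could come from reporting alone, or that the bias must favour the intervention. The documents support neither. The first depends on unknown weights. As to the second, greater awareness could raise reported risk. In addition, Recruitment sets randomisation within 24 hours and baseline within one week, so baseline answers may themselves follow allocation.

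Fourth, this is a feasibility pilot, the score is only a signal listed after feasibility and acceptability, and a component-wise analysis could sit in an SAP that is not shown. Lifestyle adherence is also collected separately under item 2(v). These arguments lower the weight of the point without removing it. The protocol itself fixes the efficacy measure as one undivided score, and which components support a statement about risk reduction is part of defining that outcome. Item 2(v) records behaviour but does not show how much of the score change came from it.

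**Conclusion.** The point holds as a conditional weakness in how efficacy measure 1 is specified. It is not a contradiction or a numerical error. The protocol does not list the score's inputs. If self-reported items carry weight, the month-2 difference between arms is open to differential reporting that assessor blinding does not address.

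Size and direction cannot be determined from the document. The percentages in the working show only how a pilot of this size would respond to an assumed shift, and they fall back to 5% if self-reported items have zero weight. The conclusion rests on two inferences: that at least one self-reported screening item enters the score, and that controls are not shown the score. It does not support a claim that any reduction seen would be mainly, or only, an artefact of reporting.

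**What to change.** In Outcome measures, item 3, efficacy measure 1:

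1. Name the inputs to the total stroke risk score and mark each as measured or self-reported.
2. Keep the change in total score as it is.
3. Add a supportive companion score at month 2, computed from measured inputs only (blood pressure, glucose, lipids, BMI/waist), with every self-reported input held at that participant's baseline value. Report it beside the total.
4. State that a between-arm difference confined to the self-reported inputs will be described as reported behaviour change.

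The companion score should inform interpretation, not act as a gate. A rule that requires it merely to move in the same direction as the total would be weak, since with no effect on the measured inputs it would be met about half the time by chance.

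**Cost.** A sentence or two in the protocol and a recalculation. The month-2 items have to be collected anyway to compute the month-2 score. The protocol does not say that individual inputs are stored or that the app can be run with some of them fixed, so both need confirming. No extra visits or participants are needed.

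**Downside.** The companion score will probably show a smaller two-month effect. It gives no credit for real changes in diet or stress that have not yet reached a measured factor, which is why it should stand beside the total score and not replace it.

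### Efficacy measure 3 counts provider encounters with no pre-trial count or care status, so routine visits add avoidable noise to an otherwise unbiased comparison

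*Protocol*

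**What the plan says.** Outcome measures, item 3 (Signal of Efficacy measures), lists three signals. The first two are changes: "Change in total stroke risk score at month 2 calculated as difference between baseline score and month 2 score" and "Change in stroke risk factor awareness score". The third is "differences in number of encounters with healthcare provider during the period of the trial in those who have either hypertension, dyslipidemia or diabetes". It is a count over the trial period only, and it is not limited by reason for visit or by whether the contact is new.

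Under Recruitment, "Risk factor screening will include measurement of blood pressure, blood glucose and lipid profile", followed by stress, diet, waist circumference and body mass index. Prior encounters and current care are not listed. The eligibility criteria do not exclude people already under a clinician. Study Participants says of the source pool: "The vascular risk factor profile of these control participants has already been assessed".

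Under Intervention, participants in that arm are shown their score and risk factors, and "They will be asked to visit their doctors /primary care clinicians to facilitate management their risk factors". Monthly reminders tell them "to follow-up with primary provider if they haven't already and especially if their risks include hypertension, diabetes, or dyslipidemia". Controls with any of the three conditions also receive advice to see a doctor, without reinforcement.

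Statistical Analysis names two-group tests of means, medians and proportions, and unadjusted odds ratios. It states that the sample size serves precision rather than power.

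**The concern.** People with hypertension, dyslipidemia or diabetes are plausibly the participants most likely to have follow-up visits already scheduled. Over two months a person in routine care may contribute one or more visits whatever the arm, while a person outside care contributes few. The count therefore mixes two groups with different means. The spread between them goes into the error variance, although one or two questions at entry could explain much of it.

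Two things are at stake. One is the precision of the estimate that the pilot is meant to hand to the next trial. The other is its readability: with no record of care status, nobody can tell afterwards whether a difference reflects more visits prompted by the intervention or a chance surplus of people already in care in one arm. An analysis plan can adjust only for what was collected, so this has to be settled in the protocol.

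**Working it through.** **Inputs from the protocol.** 50 per arm, 2 months of follow-up, and the measure restricted to people with any of three conditions. The size of that subset, the share already in care and all visit rates are not given. The protocol states no precision or power figure for this measure, so there is none to reproduce. Everything below is illustrative.

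**Assumptions.** A share s = 30%, 50% or 70% of the subset is in care. People not in care make one visit with probability 0.30 (control) or 0.60 (intervention). People in care make Poisson routine visits with mean m = 1 or 2 in both arms. Scenario A: people in care do not respond to the intervention. Scenario B: they respond equally, with one extra visit with probability 0.30 in the intervention arm.

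**Step 1, the absolute difference.**
- A: (1 − s) × 0.30 = 0.21, 0.15 and 0.09 visits at 30%, 50% and 70% in care.
- B: 0.30 visits at every share. There is no dilution.

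**Step 2, the variance that care status explains.** Within an arm, Var = (1 − s)v₀ + s·v₁ + s(1 − s)(μ₁ − μ₀)², where 0 is not in care and 1 is in care. The last term is removed by stratifying on care status. For scenario A with s = 0.5 and m = 1:
- Control: 0.5 × 0.21 + 0.5 × 1 + 0.25 × 0.7² = 0.605 + 0.1225 = 0.7275.
- Intervention: 0.5 × 0.24 + 0.5 × 1 + 0.25 × 0.4² = 0.62 + 0.04 = 0.66.
- Average 0.69375, of which 0.08125 is explained: 0.08125 / 0.69375 = 12%.

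The same formula gives these variance reductions from care status alone (large-sample values; a real trial loses a little of this):

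| Routine visits, response of people in care | 30% in care | 50% | 70% |
|---|---|---|---|
| 1 visit, none (A) | 13% | 12% | 8% |
| 1 visit, equal (B) | 17% | 16% | 11% |
| 2 visits, none (A) | 40% | 35% | 26% |
| 2 visits, equal (B) | 43% | 38% | 28% |

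**Step 3, care status and prior count together.** This was simulated with gamma-Poisson counts, 35 per arm, and 0.2 versus 0.6 mean visits among those not in care. The variance of the arm difference falls by roughly 5–18% at 1 routine visit and 26–46% at 2, across runs with and without a response among people in care. Varying how much visit rates differ between people stretches the upper ends to about 26% and 50%.

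**Step 4, chance imbalance.** With 35 per arm and half in care, the standard deviation of the between-arm difference in share in care is √(2 × 0.5 × 0.5 / 35) = 0.12. Using the control means of Step 2, a 12-point imbalance moves the raw arm difference by 0.12 × (1 − 0.3) = 0.08 visits at m = 1, or 0.12 × (2 − 0.3) = 0.20 at m = 2. The assumed effect is 0.30.

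**Step 5, would first contact be a better measure?** Power in the Step 3 setting at 1 routine visit, for 30%, 50% and 70% in care:
- No response in care: raw count 28%, 14%, 7%; first contact among those not in care 49%, 37%, 25%.
- Equal response: raw count about 40%, 32%, 27%; first contact 46%, 35%, 23%.

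The advantage of first contact depends on the assumed response of people in care. With an equal response it mostly disappears, and it reverses at 70%.

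**The case against.** Three stronger readings are tempting, and the protocol supports none of them.

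- *The comparison is biased.* A reader might infer this from the missing baseline term. Randomization is individual and by site, so routine visits balance in expectation and a post-only count is a valid contrast. Chance imbalance affects any unadjusted outcome at this size.
- *The target is a first contact, so repeat visits are the wrong thing to count.* The phrase "follow-up with primary provider if they haven't already" stands in a monthly reminder. It is naturally read as not having gone since being asked at baseline, not as never having been in care. The same sentence singles out the three conditions that define the measure 3 subset, and the reminders also cover adherence to treatment already prescribed. Someone in care who brings a visit forward to discuss the score is a success.
- *Routine visits necessarily shrink the difference.* Step 1 shows that this needs a weaker response among people in care, on which the protocol is silent.

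Other defences carry part of the way. The baseline list is not worded as exhaustive, and covariate adjustment is often left to an analysis plan, which is not shown here. Even so, nothing ties prior care or prior visits to this measure. Medication adherence is recorded, but it does not give prior visits and misses people in care without drugs. The proportion visiting their doctors is not inflated by repeat visits, but it is not split by prior care either. Finally, the pilot is not sized for power. That is fair, and it is why variance is the better yardstick here; the argument for a more precise estimate is unaffected.

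**Conclusion.** The point holds as a matter of precision and interpretability, not of validity. Measure 3 is a raw trial-period count, no pre-trial visits or care status are listed for collection, and the named tests are unadjusted. Under the stated assumptions the avoidable variance is modest at 1 routine visit per two months (roughly 5–18%) and substantial at 2 (26–46%), whether or not people in care respond. The subset size of 35 per arm, the shares in care and all visit rates are assumptions. Replacing the count by first contact among those not in care is a debatable trade-off that the protocol does not call for. Priority: minor.

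**What to change.** At consent, before randomization, ask every participant (a) whether they are already under a clinician for hypertension, diabetes or dyslipidemia, and (b) how many provider encounters they had in the previous two months. Keep the encounter count in the full subset as measure 3, and compare the arms with adjustment for baseline care status, prior two-month count and site. Report first contact among those not in care at baseline only as a supplementary descriptive breakdown.

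The timing matters. Recruitment allows up to 24 hours for randomization and up to a week for the baseline assessment, so the assessment may follow allocation. It is done by coordinators who, under Concealment of allocation, know the assignment. Answers taken then could be coloured by it.

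The cost is two self-reported questions, with some recall error, and a revised sentence for the outcome and its analysis.

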Statistical Analysis: For this pilot trial, our sample size focused on precision of estimates for a future study design rather than power of statistical tests. We will compare medians and means for continuous variables using either the Mann-Whitney's U-test or Student's t-test (paired) while categorical variables will be compared using the Chi-squared tests. A $p < 0.05$ was considered significant difference between the 2 groups. Unadjusted odds ratios were calculated for primary outcome measures.

Qualitative Interviews: We will conduct key informant interviews (KIs) with intervention participants to explore personal perspectives on acceptability of the app and video, including barriers and facilitators of its use, behavioral change efforts made to reduce stroke risk, and recommendations for revision and educational module content. Educational module content via a wireframe of app content will be shared with participants to ascertain their perceptions and recommendations for content refinement. Additionally, factors related to the social determinants of health (SDOH) will be included to better understand influence on lifestyle modification, stroke risk, and access to care and adoption of recommended health behaviors. Clinician KIs will be completed to explore their acceptance and readiness to use the app, input of current treatment practices, recommendations for educational module content, behavioral modification strategies, clinical team educational needs, and barriers and facilitators toward intervention implementation. Interviews will be audio-recorded, transcribed and translated to English when necessary, and thematically analyzed using inductive and deductive approaches.

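### The only t-test named for comparing the two independently randomised arms is a paired one, which does not fit unmatched groups

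*Protocol*

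**What the plan says.** The Statistical Analysis section gives one sentence for all continuous variables: "We will compare medians and means for continuous variables using either the Mann-Whitney's U-test or Student's t-test (paired"). The next sentence says what a p-value below 0.05 means: it "was considered significant difference between the 2 groups".

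The design is a plain two-arm parallel trial. Study design assigns 50 people to the intervention, to be "compared with a control group (n=50) who are offered one time counselling". Randomization "will be at individual level, per site". No matching, crossover or other pairing of participants is described anywhere.

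The first signal-of-efficacy measure, under Outcome measures, is "Change in total stroke risk score at month 2 calculated as difference between baseline score and month 2 score". The second is the change in the risk factor awareness score. Both are already within-person differences, one value per participant.

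**The concern.** The sentence offers two tests for the same job, and they need different data structures. Mann-Whitney requires two independent samples; a paired t-test requires each value in one column to have a natural partner in the other. This trial has no such partners between arms, so the parametric option cannot be carried out as a between-group test without inventing them.

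There is a second reading. The word may refer to each participant's baseline and month-2 values, the only natural pairs in the trial. The test would then ask whether one arm changed over time, and the control arm would play no part in it. That matters here because controls are also screened, told their risk factors and encouraged to seek treatment (Intervention section), and everyone enters with at least two risk factors. Both arms could improve over two months without any effect of the app score or the video.

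On either reading the protocol names no usable between-arm test of means for change in stroke risk score or change in awareness. At stake are a p-value that cannot be reproduced, or a claim of effect that the randomisation does not support.

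**Working it through.** The protocol gives no effect size, SD or precision target for 50 per arm, so there is no figure of its own to reproduce. The check is of what the named test does under each reading.

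**Inputs from the protocol:** 50 per arm (Study design), individual randomisation within site (Randomization), threshold 0.05 for a between-group difference (Statistical Analysis). The test is taken as two-sided; the protocol does not say.

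**Assumed, because the protocol gives none:** outcome SD of 1, pre/post correlation ρ of 0.5 to 0.8, shift common to both arms of 0.1 to 0.5 SD, no dropout.

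**Reading 1: pairing across arms**

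Take a data set with SD exactly 1 in each arm and a mean difference of 0.4.

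- Independent-samples test: t = 0.4 / √(2/50) = 0.4 / 0.2 = 2.00 on 98 df, p = 0.048. Row order is irrelevant.
- Paired test: t = 0.4 / √(2(1 − r)/50) on 49 df, where r is the chance correlation produced by the chosen pairing. With r = 0, t = 2.00 and p = 0.051. With r = +0.2, t = 0.4 / √(1.6/50) = 2.24 and p = 0.030. With r = −0.2, t = 0.4 / √(2.4/50) = 1.83 and p = 0.074.

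Re-pairing this data set at random 20,000 times gave paired p-values from 0.023 to 0.083 (central 95%; extremes 0.005 to 0.116), below 0.05 in 47% of pairings. A separate run on 30 data sets with independent-samples p between 0.045 and 0.055 gave an average range of 0.024 to 0.085.

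Long-run error rates hardly move. Over 20,000 simulated trials, type I error was 5.1% with either test, and power at a 0.5 SD difference was 0.691 paired against 0.698 independent. The defects on this reading are dependence on row order, the need for equal numbers, and 49 rather than 98 degrees of freedom.

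**Reading 2: baseline against month 2 within an arm**

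Suppose there is no treatment effect and both arms shift by s. The within-arm paired t has noncentrality s√50 / √(2(1 − ρ)) on 49 df, with critical value 2.010.

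Worked case, s = 0.3 and ρ = 0.6: SD of change = √0.8 = 0.894; noncentrality = 0.3 × 7.071 / 0.894 = 2.37; P(p < 0.05 in the intervention arm) = 0.64. Simulation of 20,000 trials gave 0.646. The chance that the intervention arm is significant and the control arm is not is 0.64 × 0.36 = 0.23.

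Chance of p < 0.05 in the intervention arm with no treatment effect:

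| Common shift | ρ = 0.5 | ρ = 0.7 | ρ = 0.8 |
|---|---|---|---|
| 0.1 SD | 11% | 15% | 20% |
| 0.2 SD | 28% | 43% | 59% |
| 0.3 SD | 55% | 77% | 91% |
| 0.5 SD | 93% | 99% | about 100% |

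In the worked case, the independent-samples test on change scores rejected in 4.9% of simulated trials, as it should, because the common shift cancels.

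**After correction**

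An independent-samples t-test on change, 50 against 50, has 98 df and critical t 1.984. The 95% interval half-width is 1.984 × √(2/50) = 0.40 SD of the change score, and power at a 0.5 SD difference is about 0.70.

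**The case against.** The strongest reply is that this is a one-word slip in a feasibility pilot. The section says "our sample size focused on precision of estimates for a future study design rather than power of statistical tests"; efficacy is the third group of outcomes and is labelled a signal; and the same sentence offers Mann-Whitney, which is a valid comparison of the change scores between arms. Random pairing across arms does not inflate type I error. The large percentages belong to the within-arm reading, which the protocol's own definition of significance disfavours, and they rest on shifts and correlations that the protocol does not supply. Regression to the mean is not certain either: risk profiles in the source pool were assessed earlier and baseline is measured afresh (Study Participants; Recruitment), so some of the regression may be over before baseline.

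Much of this stands as a limit on consequence. The fault is confined to the comparison of means, average error rates are intact on the cross-arm reading, and the within-arm figures are conditional illustrations. It does not rescue the wording. The protocol still sets a between-group p < 0.05 rule, and its Specific Aim is to determine effectiveness. Even for a pilot aimed at precision, a within-arm interval estimates the wrong quantity for the next trial. Nor is this a detail left to an SAP: a test is named, it is the wrong one, and an SAP could only put it right by contradicting the protocol. If regression to the mean is small, the time-trend problem remains, because controls are also screened and advised.

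**Conclusion.** The concern holds. The parametric test named for between-group comparisons is wrong as written for two individually randomised, unmatched arms, and neither reading makes it right.

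Read across arms, it gives a p-value that depends on an arbitrary pairing (0.023 to 0.083 for a data set whose proper p is 0.048) and cannot use all participants if completer numbers differ. Read within an arm, it does not compare the groups. The chance of a significant intervention-arm result with no effect is then about 64% at a shared 0.3 SD fall and correlation 0.6, and 28% to 95% over falls of 0.2 to 0.4 SD and correlations of 0.5 to 0.7. Those within-arm percentages rest on assumed shifts and correlations. That the test does not fit the design follows from the protocol's text alone.

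**What to change.** In Statistical Analysis, delete the word in brackets after the t-test. State that continuous outcomes, including change in stroke risk score and change in awareness score, are compared between arms with an independent two-sample (Welch) t-test, keeping Mann-Whitney as the non-parametric alternative. Preferably, though this is not needed to correct the error, use ANCOVA of the month-2 score on arm, baseline score and site, which also reflects randomisation within site. If within-arm baseline to month-2 comparisons are wanted, call them descriptive and leave them out of the sentence that defines a significant difference between groups.

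The cost is a one-line change of wording, best made before analysis. It needs no extra data or participants and no change in trial conduct.
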